* A lumbar puncture at Day 10-14 is at physician discretion, based on earlier quantitative culture results. If participants have sterile cultures from ≥ 7 days prior (i.e. Day 3 or Day 5-7 CSF culture, respectively) AND have an absence of ongoing symptoms of elevated intracranial pressure (e.g. headache), then physicians may opt to not perform the lumbar puncture.

If life-threatening (Grade 4) lab abnormalities are present or develop during the course of the study, laboratory monitoring shall occur with greater frequency for subject safety. Example:

- Creatinine: if values > 3 mg/dL (>265 mmol/L), Creatinine will be repeated at least daily until stable
- Potassium: if values ≤ 2.5 mEq/L or ≥ 6.5 mEq/L potassium will be repeated STAT and at least daily until improving

In the event of a prolonged hospitalization, the study team will continue to follow the patient daily in the hospital, with assessments, evaluation, and monitoring undertaken according to expected routine standards of care. If any subject is hospitalized at the time of their expected clinic follow-up visit (Week 4, 6, 8, or 10), the study visit will occur while hospitalized.

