9.2.1 Severity of Adverse Events

The term severity is defined as the intensity grade or level for a specific event, i.e., mild, moderate, severe, or life-threatening. Importantly, severity is *not* the same as seriousness, which is based on participant/event *outcome or action* criteria usually associated with events that pose a threat to a subject's life or functioning (ICH E2A). The *Division of AIDS (DAIDS) Table for Grading the Severity of Adult and Pediatric Adverse Events (v2.1, July 2017)* will be used. Laboratory AEs will be defined using the statistical database by DAIDS Table grading thresholds.

The Investigator will assess the severity (intensity) of each adverse event as mild, moderate, severe, or life threatening and will also categorize each adverse event as to its potential relationship to study drug using the categories of yes or no.

Assessment of severity:

The severity of all adverse events should be graded as per The *Division of AIDS (DAIDS) Table for Grading the Severity of Adult and Pediatric Adverse Events (v2.1, July 2017 or*

most current). For those adverse events not listed, the following grading system should be used:

- Mild (Grade 1): Transient symptoms, awareness of sign/symptom, but easily tolerated and no interference with patient's daily activities.
- Moderate (Grade 2): Marked signs/symptoms that interfere with a patient's usual activities, but still acceptable.
- Severe (Grade 3): Incapacitating signs/symptoms which cause considerable interference with the patient's daily activities, unacceptable.
- Life-threatening (Grade 4): Life-threatening or disabling adverse event.
- Death (Grade 5): Death-related adverse event.
 - Death from pre-existing cryptococcal infection is part of the survival endpoint, which is expected to be up to 20% of enrolled subjects. Cryptococcal meningitis deaths without other AEs should not be additionally reported as a Grade 5 AE. The objective is to discern Grade 5 deaths due to adverse events versus deaths from the progression of the pre-existing cryptococcal meningitis. Overall survival will be separately analyzed as the secondary endpoint.

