9.4 Serious Adverse Event

AEs are classified as serious or non-serious. A *Serious adverse event* is:

- fatal
- life-threatening
- requires re-hospitalization (after hospital discharge for the initial, pre-existing meningitis)
- prolonged hospitalization (due to a new AE; not due to pre-existing meningitis or HIV/AIDS)
- results in persistent or significant disability or incapacity
- results in congenital anomaly or birth defect
- an important medical event that may jeopardize the subject or may require immediate intervention to prevent one of the other outcomes listed in the definition above (e.g., anaphylaxis)

All AEs that do not meet any of the criteria for serious will be classified as *non-serious adverse events*. A standard medical problem, e.g., malaria, which in theory if untreated could result in a fatal or life-threatening event, is not by itself a SAE. If the AE is of sufficient severity to result in hospitalization, then the AE is a SAE.

Routine outpatient medical therapy for a common, expected illness in the study population (e.g., malaria, TB) is not a SAE.

All SAEs will be:

- recorded on the appropriate AE CRF
- followed through resolution by a study clinician
- reviewed and evaluated by a study clinician

Important medical events that may not result in death, be life-threatening, or require hospitalization may be considered an SAE when, based upon appropriate medical judgment, they may jeopardize the patient and may require medical or surgical intervention to prevent one of the outcomes listed above. Examples of such medical events include allergic bronchospasm requiring intensive treatment in an emergency room or at home, blood dyscrasias or convulsions that do not result in inpatient hospitalizations, or the development of drug dependency.

Death due to pre-existing cryptococcal meningitis is not a SAE. Death due to a complication of meningitis (e.g., new seizure) would be a SAE.

Prolongation of hospitalization must be due to a new AE, not the pre-existing cryptococcal meningitis or pre-existing HIV/AIDS and related conditions. A *new* AE must cause the prolonged hospitalization for this to be considered a SAE. Hospitalizations due to cryptococcal meningitis commonly may last 2-4 weeks.

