11.5 Secondary Endpoints

Key Secondary Endpoint

DOOR as ordinal ranked maximum score tested by Win Ratio.

- 18-week Survival with CSF sterility by 2-weeks
- 18-week survival with CSF culture positivity beyond 2 weeks
- Grade 3 hematological adverse event by 2 weeks
- Grade 4 hematological adverse event by 2 weeks
- Lost to follow up before 18-weeks
- Serious Adverse Event through 18 weeks (e.g. all-cause re-hospitalization, permanent neurologic deficit)
- Death by 18-weeks

Secondary Endpoints

- 1) CSF culture sterility cumulative incidence over 18 weeks using Gray's method. All persons who are non-sterile at baseline will be included with all CSF culture data considered.
 - a) CSF culture sterility at 2 weeks, 6 weeks, 10, and 18 weeks will be summarized. All persons who are non-sterile at baseline will be included with all CSF culture data considered through the relevant study visit window.
- 2) 18-week survival time

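### DOOR ranks d (Grade 4 haematological event) and f (SAE) overlap, and which one a Grade 4 blood count scores depends on a discretionary SAE call that the historical controls had made in another trial

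*Combined protocol and SAP*

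**What the plan says.** Section 11.5, repeated in Section 3.2 and the synopsis, defines the key secondary endpoint as "DOOR as ordinal ranked maximum score tested by Win Ratio". Three of its seven ranks, ordered from best (a) to worst (g), matter here:

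- Rank d, the fourth, is "Grade 4 hematological adverse event by 2 weeks".
- Rank e, the fifth, holds participants who drop out of follow-up ahead of the final visit.
- Rank f, the sixth, is any "Serious Adverse Event through 18 weeks (e.g. all-cause re-hospitalization, permanent neurologic deficit" and similar events. No haematological event is excluded.

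Some text leads from a Grade 4 count to rank f:

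- Section 9.4 lists "life-threatening" among the criteria that make an event serious. Among important medical events that may be judged serious, it names "blood dyscrasias or convulsions that do not result in inpatient hospitalizations".
- Section 7.3 applies the same adjective to laboratory values: "If life-threatening (Grade 4) lab abnormalities are present or develop during the course of the study".

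Other text keeps the count at rank d:

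- Section 8.1.1.2 requires no AE form for a laboratory abnormality unless a clinical event goes with it.
- Sections 9.6 and 9.7.1 have laboratory abnormalities graded from the statistical database and summarised apart from clinical AEs.
- Section 9.2.1 says that grade and seriousness are different concepts.

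Section 9.1 falls between the two. It keeps laboratory abnormalities in a separate category, but asks for those the investigator finds clinically significant to be reported as AEs.

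**The concern.** An ordinal endpoint needs each participant to fall in one rank by a rule that two people would apply alike. Here the worst-rank rule settles the score once an event is both Grade 4 and serious. It does not settle whether a Grade 4 count is serious. That is left to investigator judgement, and the answer moves the participant two ranks, across loss to follow-up.

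In a blinded randomised trial both arms would share the same classifiers, and the ambiguity would mostly cost precision. This trial has one unblinded arm (Section 10.3) compared with AMBITION participants (Section 4.1), whose SAEs were called by that trial's investigators. Section 11.3 defers the handling of historical controls to the Statistical Analysis Plan. The combined document contains no rule for aligning SAE calls. Reduced toxicity is a stated hypothesis (Section 11.3) and a secondary benefit (Section 2.6.2), and marrow toxicity is what ranks c and d measure. A difference in labelling would fall on those ranks and be read as a difference in safety.

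**Working it through.** The plan gives no expected DOOR distribution, sample size or power, so there is no figure to reproduce. The check has two parts.

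**1. Ranks.** Ordering a to g as 1 to 7, d is 4 and f is 6, a gap of 2. Under the worst-rank rule a participant with {d} scores d, and one with {d, f} scores f. The SAE call alone decides.

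**2. Effect of different labelling.** Let p be the rank distribution in the trial cohort and q that in the controls.

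Win ratio = Σ pᵢ·Pr(control worse than i) / Σ qᵢ·Pr(trial worse than i)

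Assumed true distribution, the same in both cohorts and not from the documents: a 30%, b 10%, c 15%, d 15%, e 2%, f 8%, g 20%. Grade 4 events stay at d in the trial. In the controls all are coded f, so q has d = 0 and f = 8 + 15 = 23%.

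- Wins: 0.30×0.70 + 0.10×0.60 + 0.15×0.45 + 0.15×0.45 + 0.02×0.43 + 0.08×0.20 = 0.4296
- Losses: 0.30×0.70 + 0.10×0.60 + 0.15×0.45 + 0 + 0.02×0.28 + 0.23×0.20 = 0.3891
- Win ratio: 0.4296 / 0.3891 = 1.104. The true value is 1.

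The same calculation with a Grade 4 share of 10% or 20% (rank a takes up the change) gives:

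| Grade 4 share | All control events coded f | Half coded f | All coded f in the trial, d in controls |
|---|---|---|---|
| 10% | 1.06 | 1.03 | 0.95 |
| 15% | 1.10 | 1.05 | 0.91 |
| 20% | 1.16 | 1.08 | 0.86 |

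I simulated 4,000 trials per setting at two-sided 5% with the Mann-Whitney test. They had 50 participants (maximum enrolment) against 164 controls (the Ugandan AMBITION intervention arm, assuming all are used). With all control events coded f, the null is rejected about 6%, 7% and 10% of the time at the three shares. With half coded f at a 20% share it is about 6%.

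**Sensitivity to the assumed distribution.** A second assumption is death 25%, lost to follow-up 3%, other SAE 10%, Grade 3 15%, and the remainder split 70/30 between a and b. With opposite coding, the null win ratio is 1.03, 1.07, 1.19 and 1.38 for Grade 4 shares of 5, 10, 20 and 30%. The reverse coding gives 0.97, 0.94, 0.84 and 0.72.

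**A uniform rule.** Under the second assumption, take a true Grade 4 share of 10% in the trial and 20% in controls. The win ratio is 1.21 if every such event is d in both cohorts and 1.27 if every one is f in both. With mixed rules it is 1.37 (trial d, controls f) or 1.10 (trial f, controls d). Consistency between cohorts matters more than which rule is chosen.

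**How common the category is.** Appendix A lists Grade 4-5 haematology events as anaemia 23+31, leukopenia 6+3, neutropenia 12+12 and thrombocytopenia 1+3. They total 91 in a trial of 177 people. These are events, not persons. They are not limited to 2 weeks and come from amphotericin plus fluconazole without 5-FC. They show that the category is not rare, and do not support any particular share used above.

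**The case against.** A reader might infer that the protocol makes every Grade 4 haematological event an SAE and so leaves rank d empty. The documents do not support that. The Section 9.2.1 wording "Life-threatening (Grade 4): Life-threatening or disabling adverse event" belongs to a fallback scale for events missing from the DAIDS table, while laboratory AEs are graded by DAIDS thresholds. The same section separates grade from seriousness. The blood-dyscrasia example in Section 9.4 is discretionary, and the Section 7.3 phrase sits in a rule about how often to repeat laboratory tests. The examples given for rank f are clinical. One can fairly argue that the most coherent reading leaves a laboratory-only count at d. That argument defeats the strong reading. It does not remove the ambiguity, because discretion over the SAE call is what makes the rank depend on the classifier.

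Three further objections limit the size. AMBITION's SAE rules are not in the documents, so neither the existence nor the direction of a labelling difference is shown. Completely opposite coding is a worst case. Section 11.7 calls the secondary endpoints mainly descriptive, and Section 11.6 makes Grade 3-5 laboratory abnormalities the key safety endpoint, so the toxicity comparison does not rest on the DOOR alone. All three stand.

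Nor should lower marrow toxicity be taken as the main benefit claimed for the reduced dose. Section 2.6.2 puts access to 5-FC first and toxicity second.

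**Conclusion.** The overlap is real. Ranks d and f are not mutually exclusive, and the text supports scoring the same Grade 4 count either way without saying which applies. If the two cohorts are labelled differently, the null win ratio moves from 1 to about 1.06 to 1.16 for a 10 to 20% Grade 4 share, by about half as much when half the events are discordant, and the other way if the coding is reversed. These figures rest on an assumed rank distribution, and the first range also on complete opposite coding. They measure how far the endpoint could move and do not estimate an actual bias. A rule applied identically to both cohorts changes little. The point is moderate: it concerns the only key secondary endpoint, which has a named test, and leaves the EFA analysis untouched.

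**What to change.** In the synopsis, Section 3.2 and Section 11.5, state that for DOOR scoring rank f excludes laboratory-only haematological abnormalities already counted in c or d. The exception is an event that also meets another Section 9.4 criterion through a clinical consequence: re-hospitalisation, hospitalisation prolonged by the new AE, or disability. Death is rank g. Derive c and d in both cohorts from laboratory values, with the same DAIDS thresholds and the same 2-week window, and not from SAE flags. Sections 9.2.1 and 9.7.1 already plan database grading for this trial, so the new step is to apply it to the controls.

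The cost is one sentence in three places and one derivation rule, with no new data from trial participants. It does require AMBITION laboratory values, whose availability the document does not state. If they cannot be obtained, report a sensitivity analysis that merges c, d and laboratory-only SAEs into one rank. That loses the distinction between Grade 3 and Grade 4 but does not depend on the SAE label for those events. Settle the rule before the cohorts are compared, so that the choice is not made with results in view.

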5.6 Study Withdrawal

By consenting to the trial, participants are consenting to receiving the study treatment, study follow-up and study data collection. However, a study subject may discontinue from further ongoing study participation at any time if:

- Subject wishes to voluntarily withdraw.
- Fulfillment of early withdrawal criterion: absolute neutrophil count < 500 x 10⁶ cells/L, thrombocytopenia < 50,000 x10⁶ cells/L, or renal creatinine clearance < 20 mL/minute

- Any unacceptable toxicity or adverse event (ie. Development of severe renal dysfunction or leukopenia on treatment).

Subjects are free to withdraw from participating in the study at any time upon request. If voluntary withdrawal occurs, the subject will be asked to complete an end-of-study evaluation and be given appropriate care under medical supervision until the symptoms of any AE resolve or the subject's condition becomes stable. The patient will be offered ongoing follow-up care at the site outpatient HIV clinic or referred to a clinic of their choice if withdrawn from the study. Participants who withdraw from Mulago hospital will not be contacted after withdrawal of consent.

Subjects may discontinue the study intervention (as per Section 5.5) and remain in the research study for safety monitoring and assessment of endpoints, receiving standard of care therapy.

Subjects withdrawing from the study will be recommended to receive standard of care therapy.

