7.5 Termination of Study

At study termination, the reason for study termination will be documented. Reasons for study termination are study completion (after 18 weeks), withdrawal of consent, death, transfer of care, or loss-to-follow-up. Analysis is by intention to treat. At the study termination visit, the following will be documented:

- Interval history
- Vital status
- AEs, updates / final outcomes

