7.5.1 Early Termination

In case of early termination, a reason for study termination will be documented. Reasons for early termination include withdrawal of consent, death, transfer of care, or loss-to-follow-up. An attempt will be made to schedule a termination visit. Assessment and laboratory evaluations for an early termination visit will be the same as the Week 18 visit.

If subjects withdraw from the study, they remain eligible for ART per national guidelines. Persons withdrawing will be encouraged to continue to receive ART from the outpatient clinic or referred to a clinic of their choice for ongoing HIV care and management of CM.

Subjects enrolled in the study but choosing to leave the hospital early against medical advice will continue to participate in the study if they wish. Additional phone calls by study personnel will encourage the subject to seek follow up HIV care and to rejoin the trial per the ongoing schedule of events. Assessment of vital status will continue via telephone calls at a minimum, unless consent is completely withdrawn.

All analysis is by intention to treat, thus anyone voluntarily discontinuing study participation must have a specific request made to them of whether continued collection of vital status (dead / alive) via an 18-week visit or a phone call at a minimum is allowable.

For persons involuntarily defaulting from study participation due to circumstances beyond their individual control (e.g., moving residence due to financial reasons, etc.), appropriate referral to local HIV-care will be arranged and a request made for a Week 18 visit. Actual transport expenses may be reimbursed in these rare occasions with prior approval of the site PI. Alternatively, phone visits may be conducted as outpatient to assess interval history and vital status.

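### The DOOR ranks loss to follow-up as an outcome level, so a difference in retention from the historical controls alone moves the win ratio away from 1

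*Combined protocol and SAP*

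**What the plan says.** The synopsis, section 3.2 and section 11.5 list the same seven levels. The best is "18-week Survival with CSF sterility by 2-weeks" and the worst is death by 18 weeks. The fourth is "Grade 4 hematological adverse event by 2 weeks", the fifth is "Lost to follow up before 18-weeks", and the sixth is an SAE through 18 weeks. Section 11.5 gives the scoring and test as "DOOR as ordinal ranked maximum score tested by Win Ratio". I read the maximum score as the worst level reached.

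Section 4.1 describes a single-arm trial of about 50 participants. Controls come from the Ugandan participants of the AMBITION trial, 163 in one arm and 164 in the other.

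On leaving the study, section 7.5 says: "Reasons for study termination are study completion (after 18 weeks), withdrawal of consent, death, transfer of care, or loss-to-follow-up". Section 5.6 adds: "Participants who withdraw from Mulago hospital will not be contacted after withdrawal of consent". Section 7.5.1 requires that anyone who stops voluntarily be asked whether vital status may still be collected.

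Section 11.6 says that dropouts and withdrawals will be summarised. No section defines loss to follow-up for the DOOR, gives an expected or historical loss rate, or plans a sensitivity analysis for it. Section 11.3 defers the details of historical comparisons to a Statistical Analysis Plan.

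**The concern.** Loss to follow-up describes what was observed, not what happened to the patient. Giving it a fixed rank has three consequences that follow from the wording alone.

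- A participant who dies after contact is lost scores level e, which beats an observed death at level g.
- A participant who is well and is lost at Week 17 scores worse than one who had a Grade 4 haematological event in the first 2 weeks.
- Section 7.5 lists withdrawal of consent and transfer of care as reasons distinct from loss to follow-up. A participant who withdraws alive and event-free on Day 6 fits no level clearly.

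In a randomised comparison with one follow-up process, the first two would tend to affect both arms alike. Here the comparator is historical, and nothing in the design equalises retention. A difference in retention would be read as a difference in benefit or harm on the only endpoint labelled key secondary.

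**Working it through.** The plan gives no expected win ratio, power or dropout rate for the DOOR, so there is no figure of its own to reproduce. The check asks what the win ratio becomes when true outcomes are identical in both groups and only loss differs. The right answer is then 1.00.

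**Assumed outcome mix** (not from the documents): a 40%, b 15%, c 12%, d 8%, f 8%, g 17%. Levels better than e total G = 0.75. Levels worse than e total B = 0.25.

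**Formula.** Let Lt and Lc be the loss in cohort and controls, unrelated to outcome. For two fully observed participants, the chance that the first is strictly better is

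S = (1 − Σp²)/2 = (1 − 0.2386)/2 = 0.3807.

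Then

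- wins W = (1−Lt)(1−Lc)S + (1−Lt)Lc·G + Lt(1−Lc)·B
- losses L = (1−Lt)(1−Lc)S + Lt(1−Lc)·G + (1−Lt)Lc·B

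so W − L = (G − B)(Lc − Lt). This is zero only when loss is equal (or G = B).

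**10% against 2%.** The shared term is 0.90 × 0.98 × 0.3807 = 0.3358.

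- W = 0.3358 + 0.018 × 0.75 + 0.098 × 0.25 = 0.3738
- L = 0.3358 + 0.098 × 0.75 + 0.018 × 0.25 = 0.4138
- Ratio = 0.90

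| Loss, cohort vs controls | W | L | Win ratio |
|---|---|---|---|
| equal | – | – | 1.00 |
| 5% vs 2% | 0.3809 | 0.3959 | 0.96 |
| 10% vs 2% | 0.3738 | 0.4138 | 0.90 |
| 15% vs 2% | 0.3666 | 0.4316 | 0.85 |
| 2% vs 10% | 0.4138 | 0.3738 | 1.11 |

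A heavier-toxicity mix (a 30%, b 10%, c 20%, d 15%, f and g unchanged) gives 0.91 for 10% vs 2% and 1.10 for the reverse.

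**Hidden deaths.** Suppose 5% of the cohort die unobserved and there is no other loss. Moving 0.05 from g to e turns ties with g into wins (0.05 × 0.17 = 0.0085) and losses to f into wins (0.05 × 0.08 = 0.004). W = 0.3807 + 0.0125 = 0.3932 and L = 0.3807 − 0.004 = 0.3767, so the ratio is 1.04. Poorer ascertainment looks like benefit.

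**Who is lost.** A second mix uses 20% deaths (9.2.1 says up to 20%) and about 30% culture positivity at Day 14 (8.2.4), with assumed SAE 10%, Grade 4 haematological 10% and Grade 3 haematological 20%. At 10% vs 1% loss the win ratio is 0.92 if loss is at random, 0.86 if only levels a–d are lost, and 1.07 if only those with an SAE or death are lost.

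**Placement of the rank.** In the same mix with random loss of 10% vs 1%, ranking the lost with death gives 0.84, ranking them with the best level gives 1.18, and leaving them out gives 1.00.

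**Sampling error.** A simulation of the first mix with no loss, 50 against 164 (section 4.1, liposomal controls), gives a null 95% range for the win ratio of about 0.63 to 1.62. In the second mix, a tie-corrected rank test at two-sided 0.05 rejects against the cohort 5.7% of the time at 10% vs 1% random loss, against a nominal 2.5%. It rejects 10.3% of the time if only levels a–d are lost. At 5% vs 1% these figures are 3.7% to 4.8%.

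**The case against.** The strongest reply is that the imbalance is assumed. That stands. A reader might infer that the controls had a different follow-up system. No section describes AMBITION follow-up or retention. The Document History records that the schedule was updated to align with the comparator's, and section 4.1 restricts controls to Ugandan participants. Telephone and home visits (7.4.1) and continued vital-status calls (7.5.1) should also reduce loss and unobserved deaths in the new cohort.

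Second, the shift is small beside sampling error, and section 11.7 calls secondary endpoints mainly descriptive. This also stands and limits the weight of the point. It does not remove it, because a shifted estimate misleads descriptively too.

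Third, placing loss between toxicity and SAE or death can be defended as a prespecified composite choice. The maximum-score rule already keeps an SAE observed before loss at level f. The gap for withdrawal and transfer could be closed by a definition. All of this is fair, but rank e would still score missing status as an outcome, with no analysis to show how much the placement matters.

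Fourth, sections 5.6 and 7.5.1 can be read together: ask at discontinuation, and make no contact after full withdrawal of consent. A reader might infer that permission given at Mulago can never be used, but the text does not say so. What remains is an ambiguity.

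**Conclusion.** The point holds in a limited form. The ranking scores missing 18-week status as an outcome, has no clear place for withdrawal or transfer, and makes the win ratio depend on relative retention. With identical outcomes and random loss, the shift is to about 0.90 or 1.11 for an eight-point difference in loss and about 0.96 for a three-point difference. All loss rates, and most of the outcome mixes, are assumptions. The documents do not show that retention differs, and the direction depends on who is lost. The effect is modest at this sample size, but the correction is cheap and should be made before analysis.

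A reader might go further and infer from the 10-week survival comparison in section 4.1 that control follow-up stops before Week 18. Control survivors would then fall into level e and the win ratio would be very large. The documents do not support this. They do not state the length of control follow-up or say that an administrative end of follow-up counts as loss, and sections 3.2 and 11.5 list 18-week survival as a secondary endpoint.

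**What to change.** In the synopsis, section 3.2 and section 11.5:

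- Treat loss to follow-up, withdrawal of consent and transfer of care, without an observed SAE or death, as missing 18-week status instead of level e. An observed SAE keeps level f under the maximum-score rule.
- Compare each pair over the follow-up that the two share, and count unresolved pairs as ties. If loss is unrelated to outcome, this treats both members of a pair alike and removes the artefact.
- Add two bounding analyses: missing counted as death, and missing counted as alive without an SAE. If loss is related to outcome, these show the range.
- Apply the same rule to the AMBITION controls, confirm that their follow-up covers 18 weeks, and report retention in both groups.

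If the sponsor prefers to keep level e, the minimum is to state that it includes withdrawal and transfer, and to add the two bounding analyses.

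Separately, reconcile sections 5.6 and 7.5.1 on whether vital status may be collected after withdrawal at Mulago, without narrowing the consent protection.

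The cost is wording in three places, a little extra analysis, more ties and slightly lower precision.
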